2. OBJECTIVES

2.1 Primary Objective

The primary objective is to evaluate the efficacy of elotuzumab when combined with KRd in terms of very good partial response or better (VGPR+) after induction in subjects with relapsed or refractory multiple myeloma, and compare to relevant historical controls. Response will be assessed based on the International Myeloma Working Group (IMWG) 2016 criteria [22].

2.2 Secondary Objectives

Secondary objectives include evaluation of elotuzumab in combination with KRd by estimating the following:

- Overall response rate (ORR) defined as the percent of subjects achieving a partial response or better per IMWG 2016 criteria [22].

- Progression-free survival (PFS) defined as the time from treatment start (Cycle 1, Day 1) until disease progression or death.
- Overall survival (OS) defined as the time from treatment start until death.
- Time to disease progression (TTP) defined as the time from treatment start until disease progression.
- Duration of response (DoR) in subjects achieving a partial response or better defined as the time from achieving a partial response until disease progression or death.
- Time to next treatment (TTNT) as defined by the time from treatment start until the start of the first subsequent anti-cancer therapy after all protocol directed therapy is completed.

2.3 Safety Objectives

The safety objectives will include evaluation of study drug administration, adverse events assessed by NCI Common Terminology Criteria for Adverse Events (CTCAE) v4.03, serious adverse events including deaths on study treatment.

2.4 Exploratory Objectives

- Explore PET/CT response as an imaging correlate end-point.
- Explore minimal residual disease (MRD) by:
 - Flow cytometry
 - NGS
- Characterize KRd-Elotuzumab synergistic activity on NK and T cell function and polarization
- Explore correlation of systemic immune profiling with measurements of clinical response such as MRD, ORR, PFS and OS by performing:
 - Cytokine profiling by multiplex protein assay
 - Blood immunotyping [including NK, NK-T and T cell subsets distribution and activation analyses] by flow cytometry
 - Bone marrow immunotyping by flow cytometry
- Explore correlation of circulating T cell receptor (TCR) repertoire immuno-sequencing by NGS with parameters of clinical response such as MRD, ORR, PFS and OS.
- Explore correlation of peripheral and medullar T cell clonal expansion with MM-PC clonal distribution
- Examine changes in biology of BM and BM plasma cells before and after treatment(s) by B cell receptor (BCR) sequencing and global gene expression profiling
- Explore immune response (with a particular emphasis on NK or T cell activation and polarization) in subjects who experience a grade ≥ 3 IRR

3. SUBJECT SELECTION

3.1 Subject Recruitment

Subjects will be recruited at Levine Cancer Institute (LCI) locations and potentially at other participating sites.

Because no dosing or adverse event data are currently available on the use of elotuzumab in combination with KRd in subjects <18 years of age, children are excluded from this study. In addition, MM is not a disease typically diagnosed in those <18 years of age.

3.2 Inclusion Criteria

Subject must meet all of the following applicable inclusion criteria to participate in this study:

1. Written informed consent and HIPAA authorization for release of personal health information signed by the subject or his/her legally authorized representative.
2. Age \geq 18 years at the time of consent.
3. Eastern Cooperative Oncology Group (ECOG) Performance Status of 0-2 (see Appendix A, Section 18.1).
4. Documented history of relapsed and/or refractory multiple myeloma per IMWG 2016 criteria [22] as defined below (biochemical and/or clinical relapse per IMWG criteria); (**NOTE:** subjects refractory to bortezomib and/or lenalidomide are eligible; subjects who previously received carfilzomib are eligible provided they experienced a minimal response or better and relapsed >60 days after completion of treatment [see exclusion criteria #2]):
 - a. Relapse is defined as progression of disease after an initial response to previous treatment, more than 6 months after discontinuation of treatment.
 - b. Refractory is defined as lack of response to previous treatment, progression of disease during treatment, or progression of disease within 6 months of discontinuation of treatment.
5. Prior treatment with one line (and no more than one line) of systemic therapy for MM; **NOTE:** A new line of therapy is considered to start when a planned course of therapy is modified to include other treatment agents (alone or in combination) as a result of progressive disease (PD), relapse, or toxicity or when a planned period of observation off therapy is interrupted by a need for additional treatment for the disease. Induction therapy and stem cell transplant followed by planned maintenance therapy (provided there is no intervening PD) are considered to be a single line.
6. Subject must have recovered from any treatment-induced toxicities to \leq grade 1 or baseline:
7. Adequate washout from previous therapy:
 - a. Prior chemotherapy is completed >3 weeks prior to day 1 of treatment (6 weeks for melphalan, nitrosoureas or monoclonal antibodies).
 - b. Autologous transplant completed (referring to day of stem cell infusion) >12 weeks prior to day 1 of treatment; allogeneic transplant >16 weeks prior to day 1 of treatment.
 - c. Prior radiotherapy completed at least 2 weeks prior to day 1 of treatment.

- d. Corticosteroid therapy at a dose equivalent to dexamethasone >4mg/day has been completed at least 2 weeks prior to day 1 of treatment.
8. Measurable disease defined as:
 - a. Serum M-protein ≥ 0.5 g/dL **OR**
 - b. Urine M-protein ≥ 200 mg/24 h **OR**
 - c. Involved free light chain (FLC) level ≥ 10 mg/dL provided serum FLC ratio is abnormal.
9. Demonstrate adequate organ function within 1 week of day 1 of treatment as defined in the table below:

System	Laboratory Value
Hematological	
White Blood Cell (WBC)	$\geq 2,000/\text{mm}^3$
Absolute Neutrophil Count (ANC)	$\geq 1,000/\text{mm}^3$ without growth factors within 1 week of day 1 of treatment
Hemoglobin (Hgb)	≥ 8 g/dL
Platelet count	$\geq 70,000/\text{mm}^3$ if bone marrow plasmacytosis of <50%; otherwise $\geq 50,000/\text{mm}^3$
Renal	
Serum creatinine OR Creatinine clearance	$\leq 1.5 \times$ upper limit of normal (ULN) OR ≥ 40 mL/min as measured by a 24-hour urine collection or estimated by the Cockcroft and Gault formula ¹
Hepatic	
Bilirubin	$\leq 2 \times$ ULN; < 3.0 for subjects with Gilbert's Syndrome
Aspartate aminotransferase (AST)	$\leq 2.5 \times$ ULN
Alanine aminotransferase (ALT)	$\leq 2.5 \times$ ULN
¹ See formula in Appendix B, Section 18.2	

10. Adequate cardiac function as defined by $\geq 45\%$ Left Ventricular Ejection Fraction (LVEF) by ECHO or MUGA within 28 days prior to day 1 of treatment.
11. Females of childbearing potential (FCBP) must have a negative serum pregnancy test (minimum sensitivity 25 IU/L or equivalent units of HCG) within 24 hours prior to day 1 of treatment, and be willing to undergo serial serum or urine pregnancy testing. **NOTE:** Females are considered of child bearing potential unless they are surgically sterile (have undergone a hysterectomy, bilateral tubal ligation, or bilateral oophorectomy) or are postmenopausal (at least 12 consecutive months with no menses without an alternative medical cause).
12. FCBP must be willing to use a highly effective contraceptive method (i.e., achieves a failure rate of <1% per year when used consistently and correctly) plus a second

contraceptive method (considered acceptable [failure rate of >1% per year] or highly effective) from the time of informed consent until 6 months after the last protocol prescribed therapy has been discontinued. **NOTE: estrogens may further increase the risk of thrombosis (beyond that associated with lenalidomide) and their use should be based on a benefit-risk decision.** For the highly effective contraceptive method, a method with low user dependency is preferable but not required (see tables, adapted from: http://www.hma.eu/fileadmin/dateien/Human_Medicines/01-About_HMA/Working_Groups/CTFG/2014_09_HMA_CTFG_Contraception.pdf).

Highly Effective Birth Control Methods

 combined (estrogen and progestogen containing) hormonal contraception associated with inhibition of ovulation 
 oral intravaginal transdermal progestogen-only hormonal contraception associated with inhibition of ovulation 
 oral injectable implantable¹ intrauterine device (IUD)¹ intrauterine hormone-releasing system (IUS)¹ vasectomised partner^{1,2} sexual abstinence³
¹ Contraception methods considered to have low user dependency
² Vasectomised partner is a highly effective birth control method provided that partner is the sole sexual partner of the FCBP trial participant
³ Sexual abstinence is considered a highly effective method only if defined as refraining from heterosexual intercourse during the entire period of risk associated with the study treatments

Acceptable Birth Control Methods

 Progestogen-only oral hormonal contraception, where inhibition of ovulation is not the primary mode of action Male or female condom with or without spermicide¹ Cap, diaphragm or sponge with spermicide¹
¹ A combination of male condom with either cap, diaphragm or sponge with spermicide (double barrier methods) are also considered acceptable, but not highly effective, birth control methods.

13. Male subjects (even those who have had a vasectomy) who are sexually active with a FCBP must be willing to use latex or synthetic condoms from the time of informed consent until 180 days after the last protocol prescribed therapy has been discontinued. The FCBP partner should also consider contraception recommendations (see inclusion #11).
14. As determined by the enrolling physician, ability of the subject to understand and comply with study procedures for the entire length of the study.

3.3 Exclusion Criteria

Subjects meeting any of the criteria below may not participate in the study:

1. Discontinuation of previous lenalidomide, carfilzomib or dexamethasone due to intolerance.
2. If previously treated with carfilzomib, lack of response, progression during or relapsed within 60 days after completion of treatment.
3. Any infection, at the time of screening, requiring systemic therapy (i.e. involving IV antibiotics) (**NOTE:** at discretion of investigator, subjects with uncomplicated urinary tract infections may be eligible).
4. Pregnant or breastfeeding (**NOTE:** breast milk cannot be stored for future use while the mother is being treated on study, and any female subject must agree not to donate eggs during the study and for 4 months after the last protocol prescribed therapy has been discontinued).
5. Has a known additional malignancy that is active and/or progressive requiring treatment; exceptions include basal cell or squamous cell skin cancer, in situ cervical or bladder cancer, carcinoma of the prostate with a current PSA value of <0.5 ng/mL or other cancer for which the subject has completed treatment, been disease-free for at least five years, and is considered by Sponsor-Investigator to be at $<30\%$ risk of relapse, or on hormonal therapy for a history of either prostate cancer or breast cancer, provided that there has been no evidence of disease progression during the previous three years.
6. Non-secretory MM.
7. Active involvement of the central nervous system by MM.
8. Prior cardiovascular cerebrovascular accident with persistent neurological deficit.
9. POEMS syndrome (plasma cell dyscrasia with polyneuropathy, organomegaly, endocrinopathy, monoclonal protein, and skin changes).
10. Had major surgery within 4 weeks prior to day 1 of treatment.
11. Plasmapheresis within 4 weeks from day 1 of treatment.
12. Treatment with any investigational drug within 4 weeks prior to day 1 of treatment.
13. Uncontrolled clinically significant illness including, but not limited to, uncontrolled hypertension (as per the most updated Joint National Committee for the Management of Hypertension definitions), symptomatic congestive heart failure (as per New York Heart Association [NYHA] class III or IV [see Appendix C, Section 18.3], uncontrolled angina

pectoris, myocardial infarction within the past 6 months, known or suspected amyloidosis, uncontrolled cardiac arrhythmia, psychiatric illness/social situations that would limit compliance with study requirements as determined by the investigator, or any other condition (including laboratory abnormalities) that would, in the opinion of the Sponsor-Investigator, place the subject at unacceptable risk if he/she were to participate in the study.

14. Known allergies, hypersensitivity, or intolerance to monoclonal antibodies or human proteins, elotuzumab or its excipients or known sensitivity to mammalian-derived products, carfilzomib or its excipients, lenalidomide or its excipients, or dexamethasone or its excipients.
15. Known human immunodeficiency virus (HIV) infection or active hepatitis A, B and/or C infection.
 - a. Subjects with resolved HBV infection (i.e. subjects who are HBsAg negative but positive for antibodies to hepatitis B core antigen [anti-HBc] and/or antibodies to hepatitis B surface antigen [anti-HBs]) must be screened using real-time polymerase chain reaction (PCR) measurement of hepatitis B virus (HBV) DNA levels. Subjects who are PCR positive will be excluded. Exception: subjects with serologic findings suggestive of HBV vaccination (anti-HBs positivity as the only serologic marker) and a known history of prior HBV vaccination do not need to be tested for HBV DNA by PCR.

3.4 Screen Failures

A subject who, for any reason (e.g., failure to satisfy the selection criteria or withdraws consent), terminates his/her study participation before receiving the first dose of study therapy is regarded as a “screen failure.” All screen failures will be tracked. Enrollment will continue until the targeted sample size in the evaluable population (Section 14.4) is achieved.

4. REGISTRATION

Following informed consent, subjects will be registered by the Coordinating Site and assigned a Study ID number. A subject is considered registered when they are assigned a Study ID number.

5. STUDY PLAN

See Schema (page III).

This single arm, open-label phase II study is designed with the primary objective of evaluating the efficacy of induction therapy comprised of 4 cycles of carfilzomib, lenalidomide, dexamethasone and elotuzumab (KRd+elotuzumab) in terms of VGPR+ in subjects with relapsed or refractory multiple myeloma, and comparing to relevant historical controls. Post induction, all subjects will undergo disease evaluation for assessment of the primary endpoint. Maintenance therapy comprised of elotuzumab and lenalidomide (R+elotuzumab) will start directly after induction and continue until relapse or progression.

This study will initially open as a single center study at LCI and additional investigational site(s) may be added following activation at the coordinating center. We anticipate subjects will be accrued over 24 months.

5.1 KRd+Elotuzumab Induction Regimen

All subjects enrolled will receive KRd+elotuzumab induction. See Section 6 for details on drug administration and dose modifications/delays. **NOTE:** Pre-hydration is required for carfilzomib as described in Section 6.3.2 and premedication is required prior to elotuzumab as described in Section 6.4.1.

Table 1: KRd+Elotuzumab Induction Regimen

Drug	Dose	Route	Schedule	4-Week (28D) Cycle
Carfilzomib ^{a,b}	20 mg/m ²	IV	D1	Cycle 1
Carfilzomib ^{a,b,c}	56 mg/m ²	IV	D8, 15	Cycle 1
Carfilzomib ^{a,b,c}	56 mg/m ²	IV	D1, 8, 15	Cycles 2-4
Lenalidomide	25 mg ^d	Oral	Once a day at bedtime on D1-21	Cycles 1-4
Dexamethasone ^g	28 mg	Oral	Once weekly ^e on D1, 8, 15, 22	Cycles 1-2
	8 mg	IV		
Dexamethasone ^{e,g}	28 mg	Oral	D1	Cycles 3-4
	8 mg	IV		
Dexamethasone ^{f,g}	40 mg	PO	Once weekly on D8, 15 and 22	Cycles 3-4
Elotuzumab ^b	10 mg/kg	IV	Once weekly on D1, 8, 15, 22	Cycles 1-2
Elotuzumab ^b	20 mg/kg	IV	D1	Cycles 3-4

^a Calculate the dose using the subject's actual body surface area (BSA) at baseline. For subjects with a BSA >2.2m², calculate the dose based upon a BSA of 2.2m².

^b If a subject's weight changes by more than 10% from induction cycle 1 day 1 the dose of carfilzomib and elotuzumab should be recalculated. This re-calculated weight should be used as the new baseline weight. **NOTE:** use the subject's actual (not ideal) body weight for dosing as per the American Society of Clinical Oncology (ASCO) guidelines in dosing of obese adult subjects.

^c **NOTE:** In subjects who enroll with a bilirubin and/or AST >1 x ULN, the starting dose of carfilzomib of 20mg/m² should be maintained and not increased to 56mg/m². The dose may be escalated to 56 mg/m² if both bilirubin and AST resolve to ≤ ULN.

^d For subjects who enroll with a CrCl between 40-50 mL/min, the starting dose of lenalidomide may be reduced to 10mg at the discretion of the investigator.

^e On days when elotuzumab is administered: 28mg PO between 3-24 hours prior to start of elotuzumab **OR** as a split dose of 12 mg 12-24 hours and 16 mg 3 hours prior to elotuzumab; 8 mg IV 45 to 90 minutes prior to elotuzumab infusion. **NOTE:** This will serve as the corticosteroid premedication for elotuzumab on days when elotuzumab is administered during induction

^f May administer 20 mg dexamethasone for subjects ≥ 75 years old

^g Oral dexamethasone may be reduced per investigator discretion. On days when elotuzumab is administered, this is allowable after C1 of induction has completed without an infusion-related reaction.

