5.2 R+Elotuzumab Maintenance Regimen

The first cycle of maintenance therapy will begin 4 weeks (28D) after the start of cycle 4 of induction. **NOTE:** premedication (including dexamethasone) is required prior to elotuzumab as described in Section 6.4.1.

Table 2: R+Elotuzumab Maintenance Regimen

Drug	Dose	Route	Schedule	4-Week (28D) Cycle
Lenalidomide	15 mg or LTD if <15mg ^a	Oral	Once a day at bedtime on D1-21	Cycles 1-n
Elotuzumab	20 mg/kg ^b	IV	D1 of each cycle	Cycles 1-n
^a LTD=last tolerated dose ^b If a subject's weight changes by more than 10% from cycle 1 day 1 of induction the dose of elotuzumab should be recalculated. This re-calculated weight should be used as the new baseline weight.				

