6.5.2.2 Dosing in Renal Impairment

Because lenalidomide is primarily excreted unchanged by the kidney, adjustments to the dose of lenalidomide are recommended in subjects with renal impairment. The recommended doses for subjects with multiple myeloma and renal impairment are shown in the table below.

Table 13: Dose Modifications for Renal Impairment

Dose modifications related to creatinine clearance only apply to Day 1 of each cycle.

Toxicity	Recommended Action
CrCl 30 to 50 mL/min	
 Ensure daily dose is no higher than 10mg every 24 hours
CrCl <30mL/min and not requiring dialysis	
 Ensure dose is no higher than 15 mg, and reduce frequency to every 48 hours
CrCl <30mL/min requiring dialysis	
 Ensure daily dose is no higher than 5 mg every 24 hours; on dialysis days, administer the dose following dialysis.

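### Table 1 footnote d and Table 13 set different default lenalidomide doses at creatinine clearance 40–50 mL/min, and the plan does not say which governs the starting dose

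*Combined protocol and SAP*

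**What the plan says.** Four places in the combined protocol and SAP bear on the lenalidomide starting dose when renal function is reduced.

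- **Section 5.1, Table 1.** Lenalidomide is 25 mg "Once a day at bedtime on D1-21" in Cycles 1–4. Footnote d, for enrolment clearance 40–50 mL/min, says that "the starting dose of lenalidomide may be reduced to 10mg at the discretion of the investigator". The same section tells the reader: "See Section 6 for details on drug administration and dose modifications/delays".
- **Section 6.5.2.2, Table 13.** For clearance 30 to 50 mL/min: "Ensure daily dose is no higher than 10mg every 24 hours". Below 30 mL/min without dialysis: "Ensure dose is no higher than 15 mg, and reduce frequency to every 48 hours". A third row covers dialysis. The text describes these doses as recommended and ties clearance-based changes to Day 1 of each cycle.
- **Section 6, introductory note.** The recommended action in every Section 6 dose modification table is left to the investigator.
- **Section 3.2, criterion 9.** Renal eligibility is serum creatinine up to 1.5 times the "upper limit of normal (ULN) OR ≥ 40 mL/min as measured by a 24-hour urine collection", or as estimated by Cockcroft-Gault. The two tests are alternatives.

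Sections 14.3.8 and 14.5.6 make relative dose intensity a safety endpoint, calculated for lenalidomide as a percentage of the intended or expected dose. Neither section says what the expected dose is for a subject with reduced clearance.

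**The concern.** Footnote d and Table 13 address the same subject on the same day from opposite starting points. In Table 1 the investigator gives 25 mg unless he or she chooses 10 mg. In Table 13 the recommendation is no more than 10 mg unless the investigator chooses otherwise. Section 5.1 sends the reader to Section 6, so a site will meet both.

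Two things are at stake. The first is consistency of a starting dose that can differ 2.5-fold (25 / 10) between comparable subjects, which bears on safety. The second is the denominator of relative dose intensity, which cannot be calculated for these subjects until someone decides which text defines the expected dose. If that is left to the analysis, it will be decided with the data in hand.

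**Working it through.** The plan states no figure on this point that needs reproducing. The check compares the texts, then works out the consequence for dose intensity and tests which clearances can enrol.

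**1. The texts side by side, clearance 40–50 mL/min, Cycle 1 Day 1**

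| Source | Default | Departure allowed |
|---|---|---|
| Table 1 with footnote d | 25 mg daily | reduction to 10 mg, investigator's discretion |
| Table 13 with the Section 6 note | at most 10 mg daily | investigator's discretion |

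Both end in discretion, but the defaults differ. A subject in this band is easy to find with the Appendix B formula. For an illustrative woman of 78 years and 60 kg with creatinine 1.0 mg/dL: (140 − 78) × 60 × 0.85 / (72 × 1.0) = 43.9 mL/min.

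**2. Expected lenalidomide dose over Days 1–21**

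- Table 1 default: 25 × 21 = 525 mg per cycle, or 2,100 mg over four cycles.
- Table 13 ceiling: 10 × 21 = 210 mg per cycle, or 840 mg over four cycles.
- A third reading lets footnote d govern only the first cycle and Table 13 the rest, with clearance unchanged: 525 + 3 × 210 = 1,155 mg.

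A subject who takes 10 mg throughout induction receives 840 mg. Relative dose intensity is then 840/2,100 = 40%, 840/1,155 = 73% or 840/840 = 100%, from identical dosing. A subject who takes 25 mg throughout scores 100% on the first reading and 2,100/840 = 250% on the last.

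Assume 40 treated subjects. Each such subject on 10 mg then moves the mean relative dose intensity by (100 − 40)/40 = 1.5 percentage points between the first reading and the last.

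**3. Which clearances can enrol**

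Because criterion 9 joins its two tests with *or*, a subject can qualify on creatinine with clearance below 40 mL/min. The table applies Appendix B at the creatinine limit of 1.5 × ULN. The documents give no ULN, so 1.0 to 1.3 mg/dL is an assumption, as are the ages and weights.

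| Subject | ULN 1.0 (creatinine 1.5) | ULN 1.2 (creatinine 1.8) | ULN 1.3 (creatinine 1.95) |
|---|---|---|---|
| Woman, 75 y, 60 kg | 30.7 | 25.6 | 23.6 |
| Woman, 65 y, 70 kg | 41.3 | 34.4 | 31.8 |
| Man, 75 y, 70 kg | 42.1 | 35.1 | 32.4 |
| Man, 65 y, 80 kg | 55.6 | 46.3 | 42.7 |

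For example, the first entry is (140 − 75) × 60 × 0.85 / (72 × 1.5) = 3,315/108 = 30.7 mL/min. Clearances below 40, and in some subjects below 30, are therefore eligible. Footnote d says nothing about them; Table 13 does.

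**4. The pointer**

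The note under Table 11 in Section 6.5.2 sends renal reductions to Section 6.5.2.2 but names Table 11, the table it sits under. The renal table is Table 13.

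**The case against.** The best reply is that there is no real contradiction. The Section 6 note makes Table 13 a matter of judgement, Section 6.5.2.2 calls its doses recommended, both texts name 10 mg for this band, and both leave the decision to the investigator. Much of that stands. A reader might infer that Table 13 is a hard cap which footnote d breaches. The documents do not support that reading, and a 25 mg start at 45 mL/min is within what they allow. What the reply does not supply is the default from which discretion departs.

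It can also be said that footnote d is the specific rule for starting and Table 13 the rule for later changes. That is a sensible way to settle it, but the plan does not say so. Table 13 is tied to Day 1 of every cycle without excepting the first. On that reading, moreover, the recommendation would change at Cycle 2 with no change in the subject's renal function.

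Two further inferences should be resisted:

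- *That the protocol leaves subjects below 40 mL/min without dosing guidance.* It does not. Table 13 covers 30–50 and below 30 mL/min, with and without dialysis, and Section 5.1 points to Section 6.
- *That the maintenance dose in Table 2, "15 mg or LTD if <15mg", is a second conflict.* Table 2 makes no statement about renal function, carries forward a last tolerated dose of 10 mg, and is subject to Section 6.5.2, which covers maintenance as well as induction.

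Finally, Section 14.5.6 also reports cumulative dose in absolute terms, so actual exposure will be visible whatever is decided. That limits the harm to the analysis but leaves the relative figure undefined.

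**Conclusion.** The point holds as an unresolved difference between two defaults for the same subject on the same day. It is a drafting inconsistency with a safety bearing. The primary analysis rule is unaffected.

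Per affected subject, the expected dose is 525 or 210 mg per cycle, and relative dose intensity on 10 mg throughout is 40% or 100%. The overall size is unknown, because the documents give no distribution of clearance and so no count of subjects in the 40–50 mL/min band. The conclusion that clearances below 40 can enrol follows from the wording of criterion 9. How far below depends on the assumed ULN, ages and weights. No view is taken on which dose is right.

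**What to change.** - Reconcile footnote d, Table 13 and the Section 6 discretion note so that one named text governs the lenalidomide starting dose for each clearance band that criterion 9 admits. Alternatively, state whether clearance below 40 mL/min is meant to be eligible. Which dose and which rule is the sponsor's clinical decision.
- In Sections 14.3.8 and 14.5.6, define the expected lenalidomide dose as the dose under that governing text. Say whether it is fixed at enrolment or updated with the Day 1 clearance of each cycle.
- In the note under Table 11, change the pointer from Table 11 to Table 13.

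The cost is amendment wording. No extra data are needed, since the Study Calendar already requires creatinine clearance at screening and on Day 1 of each cycle, and the sample size does not change.
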